7. RESEARCH METHODS

The Approach

This project will comprise a randomized, placebo- controlled, between-subjects design, where we will couple a validated behavioral paradigm on attention to social threats with an acute pharmacological challenge with oral pregnenolone (PREG) or placebo (PBO) in subjects high in PSI and test behavioral responses and neuro-active steroid levels *prior and after study oral drug administration*. In the present project, 224 PSI subjects will be randomized to a single oral dose of PREG 400mg (n=112), or placebo (PBO, n=112) to ascertain dose of administration. In this project, participants will attend a single laboratory visit. During this single session, behavioral responses and subjective feelings will be tested at two time points (once before and once after). Neuro-active steroids will be measured from blood and saliva at several points to ascertain they correlate. A group of Matched Healthy Controls (MHC) who are low in PSI (n=12) and will not receive PREG but will otherwise complete all questionnaires of the study. Participants will be recruited from the University of Chicago and in the community.

All participants must be 1) Male; 2) Aged 21-80 (inclusive); 3) High in PSI (PSI > 42, except for controls who should have a score < 42); 4) Do not meet Mini-International Neuropsychiatric Interview (M.I.N.I) criteria for psychiatric illness (except untreated major depressive disorder); and 5) BMI <30 (as ALLO levels are higher in obese than non-obese individuals). Key Exclusion Criteria: Female, as ALLO levels vary as a function of the menstrual cycle; 2) Aged < 21 or > 80; 3) Low in PSI (PSI < 42, except for controls)); 4) meet M.I.N. I criteria for psychiatric illness, besides untreated major depressive disorder; 5) Uncorrected vision; 6) Medical history of cancer; 7) Medical history of condition that might be made worse by exposure to estrogen or testosterone; 8) Recent steroid use; 9) Currently taking psychotropic medication; 10) History of seizures, neurological disorders; 11) History of TBI with loss of consciousness and/or with current cognitive impairment related to TBI; 12) Under hormonal therapy (including, but not limited to, testosterone); 13) Any unstable medical illnesses; 14) Lifetime history of bipolar disorder, schizophrenia, or psychotic disorder; 15) Current or recent (past 3 months) substance abuse or dependence; 16) Currently taking any medications that have/may have unfavorable interactions with Pregnenolone; 17) History of irregularities of heart rhythm, or heart palpitations; 18) obesity (defined as BMI>30); 19) illegal drug use as determined by urine drug screen.

Rationale: The recruitment and random assignment of young adults high in PSI to the PREG and PBO conditions allow us to ascertain the effects of PREG on PSI, depressive symptoms, and attentional biases for social threats. In addition, the recruitment of participants between the ages of 21 and 80 years will allow us to compare emotional and neurobiological findings across groups without the confounder of age effects.

Upon receipt of written consent, subjects will fill out self-report questionnaires and undertake practice on our behavioral paradigm.

During the visit, the following will occur:

- The subject will complete several questionnaires, including questions about perceived social isolation and questions about his mood.
- The subject will do a visual task on a computer.
- If the subject has low perceived isolation, the study drug will NOT be given.
- The subject will be asked to provide blood samples throughout the visit so that we

can see how his blood hormones change at different times. The experimenter will draw blood from the subject's arm three times: 1) 30 minutes after your arrival at the high-performance electrical neuroimaging laboratory, 2) one 2 and 30mn later and 3) again an hour later. About 1 teaspoon of blood will be taken each time.

- The subject will also be asked to provide saliva samples during the study at the same three times: 1) 30 mn after your arrival at the high-performance electrical neuroimaging laboratory, 2) one 2 and 30mn later and 3) again one an hour later. About 1 teaspoon of saliva will be taken each time. We ask the subject to provide saliva samples so that we can see how the samples are related to behavioral tasks and how the subject is feeling at different times in the study.
- The subject will watch a 2-hour-long relaxing movie in a quiet and relaxing environment.

Two hours after the subject takes the pill (drug or placebo), the following will occur:

- The subject will do the exact same behavioral visual task on a computer . Control subjects will perform the same tasks at the same time, except they will not take any pills.
- The subject will complete the same questionnaires again.
- The subject will wait for 30 minutes in a relaxing and quiet environment.
- The subject will be given a parking voucher or \$5 for public transportation and a \$60 monetary compensation for participating in the study.

Estimated Duration of Visit: Between 4 Hours and 4 ½ hours

In the event suicidal ideation or similar events take place during the study, the subject will be removed from the study and referred to the appropriate clinical resources.

C.2.2. Behavioral Paradigms: Subjects will be asked to perform a paradigm our lab has used to investigate social interactions on which PSI-related attentional biases may occur i.e., body language observation, facial expression, and grasping actions: Body language: As in S. Cacioppo, Bangee et al. (2014)'s study, participants will be asked to view a total of 2 blocks of pictures of body language with each block containing the 28 pictures. Each picture from each category will be presented once in a block. The order of the blocks will be randomized for each participant, but the order of the pictures within the block will be pre-determined with no more than three consecutive trials of the same picture-type presented. Prior to each trial, participants will view a white fixation cross on a black background that varied between 500 and 1500 ms. Each picture will be presented in color for 1000 ms, followed by a response slide that required a button press to move onto the inter-stimulus interval (ISI) for 500 ms. Participants will view threat and non-threat body language;

C.2.3. Psychological measures: Along with standardized assessments of symptom severity and mood/emotional state, subjects will complete the following measures, at multiple time points (e.g., before and after drug administration): The UCLA-R scale to measure perceived social isolation; Steptoe's questionnaire on objective social isolation; Hospital Anxiety and Depression Scale; Life satisfaction scale; and Demographics.

C.2.4. Study Measures: Along with various psychological measures, subjects will complete: the Edinburgh Handedness Inventory, Big Five Personality trait (short), PSI Scale, Self-esteem scale, Wong-Baker Faces Pain scale, Cacioppo Faces Social Pain scale, Paranoia Scale, Life Satisfaction Scale, Relationship/Marital Satisfaction Scale, Inclusion of the Other Scale, Columbia Suicide Severity Rating Scale, MINI, and the body image scale.

C.2.5. Drug administration: As in Sripada et al.'s 2013, study drug (PREG) and placebo (PBO) identical in appearance will be obtained from Belmar Pharmacy (Lakewood, CO), which provides certificates of analysis. A member of the research team (who is not involved in the data analyses) will randomly assign eligible subjects to the treatment group (PREG 400mg) or to the control group (PBO) through the use of a computerized random number generator. Participants will be blind.

C.2.6. Neurosteroid Analyses: To compare ALLO results with Sripada et al.'s 2013, basal serum levels will also be taken (once prior to drug administration and once two hours after oral administration of the drug study) and analyzed using a gold-standard in the literature: a gas-chromatographic mass-spectrometric (GC-MS) approach. Serum levels of pregnenolone, progesterone, 5alpha-DHP and ALLO and pregnanolone (ALLO's steroisomer and GABA-active) will be measured. As in Majewaska et al (2014), saliva samples will be analyzed using the same gold standard GC-MS approach in ALLO literature i.e., a method that allow for accurate measurement in the femtomolar range of specific neurosteroids. We will ensure that participants will refrain from smoking, eating, drinking alcoholic, caffeinated, or juicy beverages, and brushing teeth at least one hour before the first saliva sample and between saliva samples.

C.2.7. General Statistical approach:

Demographic and self-report psychological measures: Statistical analyses for demographic and self-report measures will be computed using SPSS software. Prior to inferential analyses, descriptive statistics, including distributions, means, standard deviations, skewness, and kurtosis will be generated. Data will also be examined for the pattern and mechanism of missing data. Continuous data will be tested for normality and homogeneity of variance. Potential differences between the study groups in terms of demographic and behavioral measures will be explored using multivariate analysis of variance (MANOVA) or appropriate non-parametric tests as appropriate. The overall significance level for these analyses will be at 5% using two-tailed tests and effect sizes and confidence intervals will be reported. In addition, scores at self-report questionnaires will be analyzed via a 2 (Drug Type: PREG 400mg, or PBO) x 2 (time: before, after) repeated measures ANOVA to assess for main effects and interaction effects.

Behavioral paradigms: Statistical analyses will be computed using SPSS software. Reaction times and performance data will be screened and any outliers will be removed based on each participant's trial-by-trial data. A trial will be removed if it differed by 3 standard deviations above or below the participant's mean. Prior to inferential analyses, descriptive statistics, including distributions, means, standard deviations, skewness, and kurtosis will be generated. Data will also be examined for the pattern and mechanism of missing data.

• For the *body language* paradigm: A 2 (Drug Type: PREG 400mg, or PBO) x 2 (type of stimuli: social, non-social) x 2 (nature of the stimuli: threat, non-threat) repeatedmeasures ANOVA will be performed on the reaction times and valence ratings to assess for main effects and interaction effects. P values, confidence interval, and effect sizes will be reported.

C.2.6. Power Analysis: Using G* power calculation software (Version 3.1.9.2; © Franz Faul, Edgar Erdfelder, Albert-Georg Lang, and Axel Buchner, 2006, 2009) for a within-between interaction in a repeated measures ANOVA, a total sample size of 36 for three groups will yield 95% power to detect a significant difference, with alpha = 0.05 and an effect size Cohen's *d of* 0.35 in the present project.

Note: The hormone tested in saliva and blood have the same origin from adrenals glands and gonads. Here we want to establish a correlation within the same subjects among the levels of the same neuro-active steroid determined in the blood and the saliva. We expect the hormone levels measured in saliva and in blood to be different in amount but to correlate.

Saliva samples will be analyzed using the same gold standard GC-MS approach in ALLO literature i.e., a method that allow for accurate measurement in the femtomolar range of specific neurosteroids. We will ensure that participants will refrain from smoking, eating, drinking alcoholic, caffeinated, or juicy beverages, and brushing teeth before each saliva sample.

7. Special Precautions:

Pregnenolone side effects, danger, risk, and the harm it can cause

Overstimulation and insomnia -

Irritability, anger or anxiety -

Acne can occur due to the probable conversion of this hormone into androgens

Headaches are possible with high dosages or low dosages used over several days or weeks. Possible scalp hair loss if used daily for prolonged periods. Pregnenolone converts into DHEA, which in turn converts into testosterone and possibly on to DHT. It can also be converted into progesterone.

Irregularities of heart rhythm, Heart Palpitations, even on as low a dose as 5 mg. This can be serious in the elderly or those with heart rhythm disturbances.

Unknown effects on the thyroid gland or other organs and tissues.

Special Precautions & Warnings:

Pregnancy and breast-feeding: Although there is not enough known about the use of pregnenolone during pregnancy and breast-feeding, we'll avoid this risk by testing male participants only.

Hormone-sensitive condition such as breast cancer, uterine cancer, ovarian cancer, endometriosis, or uterine fibroids might have an interaction with pregnenolone: We'll exclude participants with any history of condition that might be made worse by exposure to estrogen.

8. Participants:

We will recruit 224 men (between 21 and 80) high in PSI and 12 Matched Healthy Controls (MHC) who are low in PSI.

9. Type and Number of Experimental Subjects:

We expect to collect data from a total of 36 subjects (between 21 and 80).

10. Potential Risks and Benefits:

The study will offer no direct benefits (besides monetary benefits and potential improvement of sexual desire) to participants. The questionnaires and behavioral task also present minimal risks, which may include boredom and fatigue from looking at pictures for a few minutes and anxiety or discomfort or distress related to responding to questionnaires.

11. CONTRAINDICATIONS:

• Estrogens interacts with PREGNENOLONE

Taking estrogen along with pregnenolone might cause too much estrogen to be in the body.

Some estrogen pills include conjugated equine estrogens (Premarin), ethinyl estradiol, estradiol, and others.

Progestin interacts with PREGNENOLONE

Progestins are a group of hormones. Taking other hormones along with progesterone pills might cause too much hormones in the body. This could increase the effects and side effects of hormone pills.

• Testosterone interacts with PREGNENOLONE

Taking pregnenolone along with a testosterone pill might cause too much testosterone in the body. This might increase the chance of testosterone side effects.

12. Monitoring of Safety:

A researcher will be present with participants during the duration of the experiment. While participants are in a separate room sheltered, researchers will monitor participants' wellbeing via cameras and microphones within this room. Participants will have the ability to communicate with researchers through these microphones and may opt out of participation at any time. Participants will also be provided with the IRB's contact information on the consent form, and we will contact IRB should any adverse effects occur.

Regarding pregnenolone's side effects: Subjects will be directed to call a member of the study team if they believe they are experiencing any side effects within the 12 hours following the end of the study.

13. Payment:

Participants will receive the \$60 monetary compensation (Internal Fundings/No Fund) for their participation in the entire study. If participants should decide to opt out of participation after the beginning of the study, their participation would be pro-rated (\$15 per hour).

14. Informed Consent:

We are asking to waive first consent form to do a brief phone interview and see whether the participants are eligible. Then the participants will come to the University of Chicago and read, understand and sign the written consent form attached in this IRB application. Participants must acknowledge understanding of procedures, risks, and benefits by signing this consent form before the study can proceed.

15. Confidentiality:

De-identified data will be stored in locked drawers or cabinets or on password-protected computers within the HPEN laboratory or on password protected University of Chicago server, such as UChicago Box. Data may be used in publications, but no personally identifiable information will be disseminated outside of researchers included in this protocol.

16. Recruiting Methods:

Subjects will be recruited via Flyers posted on Campus, sona or websites, such as craigslist.

17. Primary Physician Notification:

[name], M.D.

18. Anticipated Coordination between Inter-Departmental Faculty:

[name]., [name]., and [name]. are all members of the Department of Psychiatry and Behavioral Neuroscience. [name] is the Director of the Center for Cognitive and Social Neuroscience. These researchers will coordinate extensively on this project.

19. Pregnancy Test: N/A. The present research only includes male participants.

20. Drug Test:

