Reducing PSI, attentional biases, and depressive symptomatology through the use of a pharmacological treatment may, therefore, have potential benefits for health and well-being. Until now, a main challenge for physicians and mental health clinicians has been to become sufficiently informed about the scientific definition of PSI (or loneliness) so that other mental disorders were not mistakenly diagnosed and treated when PSI was either the primary presenting problem or the cause of the depression for which treatment was sought⁴⁴. For decades, many clinicians believed that PSI was simply an aspect of depression with no conceptual distinctions worthy of study¹. There is now considerable evidence showing that PSI and depression (as well as other factors such as introversion, neuroticism, objective social isolation, & social support) are separable and that PSI increases the risk for (or leads to) depression. For instance, even after controlling for objective social isolation and other potential confounding factors, PSI contributes to a constellation of physical and psychiatric dysfunctions⁴⁴⁻⁴⁸. PSI is also a risk factor for alcoholism, suicidal thoughts, aggressive behaviors, social anxiety, and impulsivity. In addition, PSI is a risk factor for cognitive decline and the progression of Alzheimer's Disease, recurrent stroke, obesity, increased vascular resistance and elevated blood pressure, increased hypothalamic pituitary adrenocortical (HPA) activity, diminished immunity, an under-expression of genes bearing anti-inflammatory glucocorticoid response elements and an upregulation of proinflammatory gene transcripts, and premature mortality. Moreover, meta-analyses indicate that cognitive/behavioral interventions have proven to be largely ineffective. Thus, a pharmacological treatment for PSI is timely needed. Despite its public health importance, there is no pharmacological treatment for PSI. In addition, a key neurobehavioral characteristic of individuals high in PSI is an increased implicit attentional bias for social threats, which has been linked to an early evoked neurophysiological response and underlie unsuccessful social connections and social withdrawal. This focus on self-preservation reinforces Cacioppo and colleagues' seminal evolutionary model of PSI⁸ that emphasizes the role of hyper-vigilance to social threats as a mechanism promoting short-term survival but also as having long-term costs for health and wellbeing.

3. Innovation

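### Untreated major depression is allowed at entry, but M.I.N.I. depression status is used in neither the allocation nor the models, so no planned analysis can show which men a result came from

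*Combined protocol and SAP*

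**What the plan says.** **Eligibility (section 7, Research Methods).** Inclusion item 4 reads "Do not meet Mini-International Neuropsychiatric Interview (M.I.N.I) criteria for psychiatric illness (except untreated major depressive disorder". The matching exclusion bars men who meet "criteria for psychiatric illness, besides untreated major depressive disorder". The two agree: untreated MDD is the only M.I.N.I. diagnosis allowed in. No cap or expected share is given.

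**Allocation (C.2.5, Drug administration).** Eligible men are assigned "through the use of a computerized random number generator". No strata, blocks or covariates are named. Section 7 gives the size: "224 PSI subjects will be randomized to a single oral dose of PREG 400mg (n=112), or placebo (PBO, n=112".

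**Analysis (C.2.7, General Statistical approach).** For questionnaires, "scores at self-report questionnaires will be analyzed via a 2 (Drug Type: PREG 400mg, or PBO) x 2 (time: before, after) repeated measures ANOVA". The body-language model has drug, stimulus type and threat as factors. Neither has MDD as a factor, covariate, interaction or subgroup. The exploratory MANOVA between groups covers demographic and behavioural measures and does not name M.I.N.I. status. The Hospital Anxiety and Depression Scale (HADS) is taken before and after dosing (C.2.3) and is analysed only as an outcome.

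**Rationale.** Section 2 (Purpose) says "There is now considerable evidence showing that PSI and depression" can be told apart, and goes on to say that PSI raises the risk of depression or leads to it. Hypothesis 2A (Aims & Hypotheses) predicts fewer depressive symptoms and less attentional bias under pregnenolone in men high in PSI.

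**The concern.** The protocol treats loneliness and depression as distinct conditions and wants a drug treatment for loneliness. It also cites earlier evidence that pregnenolone relieves depressive symptoms in humans (section 1), so a larger benefit in depressed men is plausible on its own premises. The planned drug terms average over men with and without MDD. If the pooled result is positive, readers will ask whether lonely men without MDD benefited. If it is null, they will ask whether an effect in some men was diluted by the others. The trial will hold the data to address both questions, but nothing in the plan uses them.

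**Working it through.** **The plan's own figure.** There is none on MDD. The only sample-size figure is 36 subjects in three groups for 95% power (Power Analysis, the second section numbered C.2.6). It reproduces for a within-between interaction with two time points if 0.35 is read as Cohen's f and the within-person correlation is taken as 0.5 (an assumption): minimum N is 35, rounded to 36, with power 95.75%. It makes no allowance for MDD.

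**Inputs.** From the documents: 112 per arm, two-sided alpha 0.05. Assumed: MDD share p from 10% to 50%; effect in MDD men of 0.8 SD or 0.4 SD, and zero in the others; a common SD. With two time points the drug-by-time test is equivalent to a two-sample t test on change scores, so for questionnaires the SD is that of the change score.

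**1. Dilution.** Pooled effect = p × effect in MDD men. Power is from the two-sample t test at 112 per arm.

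| MDD share | Pooled effect (0.8 SD in MDD) | Power | Pooled effect (0.4 SD in MDD) | Power |
|---|---|---|---|---|
| 10% | 0.08 | 9% | 0.04 | 6% |
| 20% | 0.16 | 22% | 0.08 | 9% |
| 30% | 0.24 | 43% | 0.12 | 15% |
| 50% | 0.40 | 85% | 0.20 | 32% |

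**2. What stratum estimates could show at N = 224.** The 95% half-width in men without MDD is 1.96 × √(2/(112(1−p))); in men with MDD it is 1.96 × √(2/(112p)). The SE of the drug-by-MDD difference is √(4/(224p) + 4/(224(1−p))). The smallest difference detectable with 80% power is 2.80 × that SE.

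| MDD share | Half-width, no MDD | Half-width, MDD | SE of drug × MDD | Detectable drug × MDD |
|---|---|---|---|---|
| 10% | 0.28 SD | 0.83 SD | 0.445 | 1.25 SD |
| 30% | 0.31 SD | 0.48 SD | 0.292 | 0.82 SD |
| 50% | 0.37 SD | 0.37 SD | 0.267 | 0.75 SD |

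**3. Chance imbalance without strata.** The SD of the difference in MDD share between arms is about √(p(1−p) × 2/112). At p = 0.3 this is 0.061, so the 95% range is 1.96 × 0.061 = ±12 percentage points. At shares of 10%, 20% and 50% the range is about ±8, ±10 and ±13 points.

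**4. If the total is 36.** Taking out the 12 controls leaves 24, or 12 per arm. At a 30% share that is 12 × 0.3 = 3.6, about four MDD men per arm. The half-widths are 1.96 × √(2/3.6) = 1.46 SD with MDD and 1.96 × √(2/8.4) = 0.96 SD without, too wide to inform.

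**The case against.** The strongest reply is that nothing here is biased. Randomisation balances MDD on average, the stated target is men high in PSI, and the protocol deliberately keeps those with untreated MDD. Because it regards depression as partly a consequence of loneliness and lists depressive symptoms among the things to be reduced, relief of depression in lonely men is part of its aim. This stands: a reader might infer that the comparison is confounded by depression, and the documents do not support that.

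A reader might also infer that a benefit confined to depressed men would be reported as an effect in PSI. That goes too far. Under the larger assumed effect, most trials with a share of 30% or less would find nothing, and at 0.4 SD that is so at every share tabulated. Nor is the plan blind to the difference between loneliness and depression: the UCLA-R loneliness scale and HADS are separate measures, and a change on depression alone would appear as such. That distinguishes outcomes, however, not the men who benefited.

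The imbalance argument is weak for questionnaires, since a stable difference in level between MDD and non-MDD men cancels in the drug-by-time term; only a different course over the visit would matter. The body-language model has no time factor, so that cancellation does not carry over to it. Two further readings lack support: C.2.5 does not say the randomisation is simple, only that no strata are named; and absence of an MDD diagnosis is not absence of depressive symptoms.

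Finally, the subgroup analysis is limited. Even at 0.8 SD, the drug-by-MDD test has about 43% power at a 10% share and 78% at 30%. This is a reason to present stratum estimates as descriptive, not to omit them.

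**Conclusion.** The omission is real, and it affects interpretation and precision, not validity. The pooled contrast answers the question for men high in PSI. As planned, it cannot show whether a positive result came mainly from men with MDD or whether a null result reflects dilution. The possible dilution is large: an effect of 0.8 SD in MDD men alone becomes 0.08 to 0.40 SD overall, and 0.4 SD becomes 0.04 to 0.20 SD. Both effect sizes and the 10% to 50% share are assumptions. The precision forgone cannot be sized, because the documents do not say how strongly MDD status predicts the outcomes.

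It is tempting to conclude that any claim about PSI must rest on men without MDD alone. The documents do not require this, and it would move the conclusion to a smaller group in which a zero estimate would still leave effects of about 0.3 SD possible.

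**What to change.** - **C.2.5:** stratify the 1:1 allocation list by M.I.N.I. MDD (yes/no).
- **C.2.7, models:** add MDD status as a baseline covariate. In the questionnaire model include its time term, because a main effect alone leaves the drug-by-time test unadjusted; for the same reason include its stimulus terms in the body-language model.
- **C.2.7, reporting:** keep the overall pregnenolone–placebo contrast as the main result. Pre-specify that contrast with its 95% CI in men with and without MDD as supportive and descriptive. Label drug × MDD exploratory, since at N = 224 it detects only about 0.75 to 1.25 SD with 80% power.
- **Conclusions:** state whether the effect is also seen in men without MDD, without resting PSI claims on that estimate alone.
- **Sample size:** reconcile the 224 randomised men (sections 7 and 8) with the 36 subjects in the Power Analysis and section 9. At 36 the stratum estimates are not worth having.

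The cost is a two-stratum list and a few model terms, using a diagnosis already needed for eligibility. The price is slightly more allocation work and wide subgroup intervals (about ±0.28 to 0.37 SD in men without MDD at N = 224). If allocation has begun, the C.2.7 changes can still be fixed before unblinding.

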4. Rationale for using pregnenolone (PREG), as opposed to ALLO: The rationale for a PREG approach is that PREG is an ALLO precursor that is lipophilic and readily crosses the blood brain barrier—a characteristic that makes it the first line of pharmacological treatment for PSI. PREG deficiency leads to depression and even suicide and there are also studies showing impairment of cognition and memory and replacement therapy reverses these effects. PREG is the precursor of neurosteroids and also TSPO agonists that increase levels of PREG and downstream steroids, including ALLO have been suggested for anxiety/depression treatment and tested in clinical trials and these molecules show advantages for the treatment of several neuropathologies^{63,64}. It is important to emphasize that in this study the dose-response design followed by determining the levels of neurosteroids (e.g., ALLO) aims at a normalization of the PSI-induced downregulation of the serum neuro-active steroid levels rather than increasing them to supraphysiologic levels. Therefore, measuring neuro-active steroids immediately after completion of treatment will guide eventual adjustment of doses and therefore a better utilization of resources during the Present project. The novel application of PREG in the present study is also reinforced by the compelling findings by Sripada and colleagues, who showed an acute, oral dose (400mg) of PREG up-regulate ALLO in young adults (age between 18-32) and reduce activation of brain areas underlying negative emotions processing. An alternative means of increasing ALLO would be to administer it directly. However, such approach would increase the risk of undesirable side effects (e.g., sedation) as it would globally impact ALLO levels even in brain regions where levels are physiologically low. Also, while synthetic neurosteroids (e.g., Ganaxolone) offer another potential approach, they are currently under development or require further testing for potential medical use in humans. Because SSRI, such as fluoxetine (FLX), are also known to elevate ALLO levels, a FLX approach could have been also considered. However, FLX has a low response rate, which varies from 30-50%, and a constellation of undesirable side effects. Thus, pre-clinical work signifying PREG, a generally well-tolerated dietary supplement, up-regulates ALLO suggests it is a viable approach to engage ALLO inhumans. Clinical trials that have used a PREG approach on negative emotion processing, schizophrenia, or on inflammatory diseases, consistently show that PREG 25-500 mg/day has minimal side effects, and does not affect weight, heart rate, blood pressure (even in patients with hypertension), menstrual cycle, or glucose levels (either in diabetics or non-diabetics.

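### The protocol says that enrolling ages 21 to 80 removes age as a confounder; it adds age variation, and no stated analysis adjusts for age

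*Combined protocol and SAP*

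**What the plan says.** All references are to the combined protocol and SAP.

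- **Eligibility (section 7, Research Methods):** "Aged 21-80 (inclusive").
- **Rationale (same section):** it opens with "The recruitment and random assignment of young adults high in PSI". Its next sentence says that the 21 to 80 range lets the study "compare emotional and neurobiological findings across groups without the confounder of age effects".
- **Source study (section 4, rationale for using pregnenolone):** the single-dose study on which the dose rests enrolled "young adults (age between 18-32").
- **Allocation (section 7):** "224 PSI subjects will be randomized to a single oral dose of PREG 400mg (n=112), or placebo (PBO, n=112"). C.2.5 assigns subjects "through the use of a computerized random number generator" and mentions no stratification by age.
- **Self-report analysis (C.2.7):** a "2 (Drug Type: PREG 400mg, or PBO) x 2 (time: before, after) repeated measures ANOVA", with no covariate.
- **Task analysis (C.2.7, body language paradigm):** drug by stimulus type by threat, with no covariate and no time factor.
- **Demographics (C.2.7):** differences between groups are explored by MANOVA. No adjustment follows from the result.
- **Controls (section 7, Aims and section 8):** 12 men low in PSI, described as matched. No matching variable is named.
- **Hypotheses (Aims):** 1A expects ALLO on PREG to reach the level of the matched controls. 2B expects negative correlations of ALLO with depressive symptoms and with attention to social threat. No model is given for either.

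**The concern.** The reasoning in the Rationale runs the wrong way. A narrow age range limits age effects and a wide one admits them. The sentence would suit a young-adult sample, which is what the sentence before it still describes, but not men up to 80. The protocol itself treats age as a potential confounder, and the sentence in effect stands in for any handling of age in the analysis.

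Two things are at stake. The first is precision, wherever a test rests on differences between subjects rather than within them. The second is validity where randomisation offers no protection: an age gap between the PSI men and the 12 controls could be read as an effect of PSI or as failure to normalise, and age could produce an ALLO-symptom correlation with no direct link between the two.

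**Working it through.** The plan gives no figure for age effects, so there is none to reproduce. The check is a reading of each analysis, followed by arithmetic on stated assumptions.

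**1. How much age variation the range admits.** Assume uniform ages, so SD = range/√12.
- 21 to 80: 59/√12 = 17.0 years.
- 18 to 32 (source study): 14/√12 = 4.0 years.
- Variance ratio: (59/14)² = 17.8, about 18 times.

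**2. Where a constant age effect cancels.** Write a subject's outcome as a term in age plus the rest, with the age term the same before and after dosing.
- Drug by time: with two time points this is a comparison of after-minus-before changes, and the age term drops out.
- Drug by stimulus type or threat: this compares within-subject differences between stimuli, and the age term again drops out.
- Drug main effect in the task ANOVA: this compares subject means between arms. There is no time factor, so the age term stays in the error.

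**3. Power for that between-subject contrast.** Inputs: 112 per arm (section 7), two-sided 5% (C.2.7) and a standardised difference of 0.35. The last figure is borrowed from the Power Analysis for illustration; that calculation was for a different test. If age correlates r with the outcome, adjustment reduces the residual SD by √(1−r²), so the effective difference is 0.35/√(1−r²). The documents give no r, so a range is assumed. Power is from the noncentral t distribution with noncentrality d√(112/2).

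| r (assumed) | Effective d | Power |
|---|---|---|
| no adjustment | 0.350 | 74.1% |
| 0.1 | 0.352 | 74.6% |
| 0.2 | 0.357 | 75.9% |
| 0.3 | 0.367 | 78.0% |
| 0.4 | 0.382 | 81.2% |
| 0.5 | 0.404 | 85.3% |

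**4. Age gap between groups.** SE of the difference in mean age = 17.0 × √(1/n₁ + 1/n₂), with uniform ages and no age matching.
- PREG v PBO, 112 v 112: 2.3 years (95% chance range about ±4.5).
- PREG arm v controls, 112 v 12: 5.2 years (about ±10.1).
- All PSI v controls, 224 v 12: 5.0 years (about ±9.9).

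The last two lines apply only if the controls are not in fact matched on age.

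**5. Hypothesis 2B.** If age correlates with ALLO and with the outcome at size r each, and nothing else links them, their correlation has size r². It is negative, as the hypothesis predicts, if the two age associations run in opposite directions. The chance that a two-sided 5% test rejects, by Fisher's z, uses mean artanh(r²) × √(N−3). N = 236 is 224 + 12. Section 9 instead expects 36 subjects in total, so both are shown.

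| r (assumed) | r² | N = 236 | N = 36 |
|---|---|---|---|
| 0.2 | 0.04 | 9% | 6% |
| 0.3 | 0.09 | 28% | 8% |
| 0.4 | 0.16 | 69% | 15% |
| 0.5 | 0.25 | 97% | 31% |

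**The case against.** The strongest reply is that the main comparison is randomised. Random assignment removes age bias between PREG and PBO in expectation, and at 112 per arm a mean age gap over 5 years has about a 3% chance under the uniform-age assumption. The outcomes are also measured before and after dosing, and the threat hypothesis concerns within-subject contrasts, so stable age differences are already absorbed. This stands. A reader might infer from the false sentence that PREG versus PBO is biased by age, or that adding age would raise power across the planned tests. The documents support neither. Adjustment would help the drug-by-time test or the threat interactions only if age altered the change or the threat bias itself, and nothing in the documents addresses that.

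It can also be said that no lower limit on the age correlation is known. This stands too: at r = 0.1 the gain is about half a percentage point.

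A third reply is that the controls are called matched and that the MANOVA would bring an age gap to light. In part this holds. A reader might infer that the controls are confounded by age, but the documents do not show it. They show only that the matching variables are unnamed, and the 5-year SE depends on age not being one of them. The MANOVA could detect a gap but leads to no adjustment, and with 12 controls it would be a weak check. Neither matching nor the MANOVA does anything for the correlations in Hypothesis 2B.

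**Conclusion.** The concern holds in a limited form. The sentence in the Rationale is wrong for a 59-year range and clashes with the description of the sample just before it. No stated analysis adjusts for age.

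The consequences are modest for the randomised comparison, which remains valid. The only precision loss that follows from the stated models is in the Drug main effect of the task ANOVA, where adjustment would add between about half a point and 11 points of power over the assumed range of r.

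The more serious exposure is outside the randomisation. In the comparison with the 12 controls, chance alone gives an SE of about 5 years for the age gap if age is not matched and ages are uniform. In Hypothesis 2B, age can produce a correlation of size r², which is negligible at small r but likely to be declared significant at r = 0.4 or more with 236 men. These figures rest on assumed correlations and an assumed age distribution, so they show what is possible rather than what will happen. The change should be made because it is nearly free, and because an adjustment chosen after the exploratory MANOVA would be post hoc.

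**What to change.** 1. Delete the sentence claiming freedom from age confounding, and reconcile the reference to young adults with the 21 to 80 eligibility range.
2. Prespecify continuous age as a covariate in the body language task ANOVA and in any PSI versus control comparison, including the ALLO comparison in Hypothesis 1A once its model is written.
3. For Hypothesis 2B, prespecify age-adjusted partial correlations.
4. Name age as a matching variable for the healthy controls and say how the matching is done.

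Age need not be added to the drug-by-time self-report model for this reason.

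The cost is a few lines of text and one degree of freedom per model. Age is already recorded, through eligibility and the demographics form, so no new data are needed.
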